2.12 Baseline and Screening Definitions

2.12.1 Baseline

Unless otherwise specified, Baseline is defined as the value of a variable at the Day 1/Baseline Visit. If there is a missing value at the Day 1/Baseline Visit, Baseline is defined as the last available non-missing value on or before and ≤ 10 days prior to the first dose of blinded study medication.

For randomized but not treated subjects, Baseline is defined as the value at the Day 1/Baseline Visit; if missing, it is defined as the last available non-missing value on or before and ≤ 10 days prior to the date of randomization

Some laboratory tests are assessed by both the central laboratory and a local laboratory. In these cases, the following baseline values are defined:

- Local Baseline (Bsl_L) is defined as above using only local values
- Central Baseline (Bsl_C) is defined as above using only central values

- Central/Local Baseline (Bsl_CL) is defined as the Central Baseline (Bsl_C) if available, and as the Local Baseline (Bsl_L) if the Central Baseline is missing
- Local/Central Baseline (Bsl_LC) is defined as the Local Baseline (Bsl_L) if available, and as the Central Baseline (Bsl_C) if the Central Baseline is missing

In general, if an analysis includes only local laboratory test results for a specific laboratory test value, Bsl_L is used to calculate change from Baseline and is used as the baseline covariate in models; if the analysis includes only central laboratory test results, Bsl_C is used; if the analysis includes both central and local test results, Bsl_CL or Bsl_LC is used.

Tables and figures will specify what baseline is being used for the table or figure.

The following are specific exceptions to these rules:

- For eGFR, Bsl_CL is defined differently than for other laboratory parameters. The definition is: the value of the Central Baseline (Bsl_C); if missing, the value of the Local Baseline (Bsl_L); if missing, the value at Day 3, with preference for the central value
- Urine ACR is assessed only by the central laboratory, and is collected only during Run-in, at Day 3, Week 2, Week 18, and at each 3-month visit during the Double-blinded Treatment Phase. For analyses of proteinuria, Baseline is defined as the central value of urine ACR at the Day 3 Visit.

2.12.2 Screening

Unless otherwise specified, the screening value of a variable is defined as the value of the variable at the Screening Visit. If there is a missing value at the Screening Visit, the screening value is defined as the earliest available non-missing value on or before the first dose of patiromer in the Run-in Phase and on or after the first date in the Screening period. If a subject was screened more than once, only the last screening that was associated with entry into Run-in will be considered. If the subject never entered Run-in, only the last screening period for the subject will be considered.

For laboratory tests that are assessed by both a local and a central laboratory at Screening, the following Screening values are defined:

- The Local Screening value (Scr_L) is defined as above using only local values
- The Central Screening value (Scr_C) is defined as above using only central values
- The Central/Local Screening value (Scr_CL) is defined as the Central Screening value (Scr_C) if available, and as the Local Screening value (Scr_L) if the Central Screening value is missing

If an analysis includes only local laboratory test results, Scr_L is used to calculate change from Screening; if the analysis includes only central laboratory test results, Scr_C is used; if the analysis includes both central and local test results, Scr_CL is used.

NT-proBNP is assessed by the local and central laboratories at Screening, but after Screening is assessed only by the central laboratory, at Week 18 and at each 3-month visit during the Double-blinded Treatment Phase. For analyses of change from Screening, the Scr_CL value will be used.

Two sets of subgroups are defined by laboratory screening values. These are the CKD and NT-proBNP subgroups. In both cases, Scr_CL will be used to determine subgroup assignments.

2.13 Study Day and Visit Windows

The first date of dosing with the study medication (patiromer/placebo) will be used as the Reference Date for Study Day calculation.

The Study Day for date of first dosing is Day 1. The Study Day for all other study events is defined as follows:

- If a date is prior to the Reference Date, Study Day is defined as [date] - [Reference Date], so the Study Day for the day before date of first dose is defined as Day -1.
- If a date is on or after the Reference Date, Study Day is defined as [date] - [date of blinded study drug] +1; hence, the Study Day for the day after first dose is defined as Day 2.

Unless otherwise specified, summaries by visit will use the visit weeks/months reported in the database and include the results collected at scheduled visits.

The analyses which are not limited to scheduled visits (e.g. adverse events, incidence of laboratory test values within a given range, and time to event analyses), will include all available values of the variable of interest, irrespective of whether it was collected at a scheduled or unscheduled visit. For central laboratory data, the visit information from the central laboratory will be used to determine whether a visit is scheduled or unscheduled.

2.14 Handling of Missing Data

Missing data will be reflected primarily through the use of censoring for incomplete follow-up. The approach will depend on the particular analysis.

2.14.1 Missing Information for Adverse Events

For subjects with the missing information for adverse events, the following imputation rules will be applied:

- An adverse event with onset date equivalent to the first dosing date will be considered to be treatment-emergent unless there is evidence to conclude that it is not.
- An adverse event with missing severity will be assigned to the highest severity observed for the subject, among all events with the same preferred term; if there are no other adverse events (AEs) with same preferred term and non-missing severity, the adverse event will be counted as severe.
- An adverse event with missing relationship to study drug (patiromer/placebo) will be assigned to possible relationship (i.e. related).

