8.2 Treatment Phase (Double-Blinded) Procedures

Subjects who meet all randomization criteria (see Section 5.4) within the 12 weeks of the Run-in Phase (single-blinded) may be randomized on the same day in which they qualify, and all assessments performed at the visit in the Run-in Phase when they qualified will be considered the Baseline assessments and will not be repeated. The qualifying Run-in Phase visit will become the Day 1/Baseline Visit.

If a subject cannot be randomized on the same day the randomization criteria were met, then the subject should be randomized within 1 week and all assessments described in Section 8.2.1 will be repeated on the day of randomization.

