12.9 Safety Evaluations

The following safety variables will be summarized using the safety set:

- AEs and SAEs (coded using Medical Dictionary for Regulatory Activities (MedDRA); see Study Manual for MedDRA version), including all-cause mortality
- Slope of eGFR change during the study will be estimated and compared between treatment groups using a repeated measures analysis with time treated as a continuous variable
- Decline in eGFR >50% or ESRD, renal death, or need for dialysis
- Laboratory parameters other than those defined as efficacy endpoints

AE summaries will be provided separately for: (1) AEs with start date on or after first dose date during the Run-in Phase and on or before the date of randomization; and (2) AEs with start date on the day after randomization. Summaries will consist of counts (%) by system organ class (SOC), preferred term (PT) and severity in the Run-in Phase, and by SOC, PT, severity, and treatment in the blinded withdrawal phase. The following types of AEs will be summarized:

- All treatment-emergent adverse events (TEAEs)
- TEAEs related to study medication (patiromer/placebo) and to RAASI
- TEAEs leading to study medication discontinuation (patiromer/placebo) and to RAASI discontinuation
- SAEs

A listing of AEs will be provided, to include verbatim term, PT, SOC, intensity/severity, relationship to patiromer/placebo, and to RAASI, whether serious, onset/end date, action taken and outcome of event.

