APPENDIX A: IMPUTATION OF DATES

1 Imputation of Missing/Partially Missing Adverse Event Dates

1.1 Incomplete Start Date:

Partially missing AE start/stop dates will be imputed in the analysis dataset model (ADaM) dataset for AEs, according to the rules below. However, listings of AE data will present the date as is, with missing date components left blank.

If the AE end date is complete with no missing year, month, or day, and a partially missing start date imputed by the rules below is after the AE end date, then the imputed start date will be equal to the end date.

Missing day and month

- If the year is the **same** as the year of the first dosing date, then the day and month of the first dosing date will be assigned to the missing fields.
- If the year is **prior to** the year of first dosing date, then December 31 will be assigned to the missing fields.
- If the year is **after** the year of first dosing, then January 1 will be assigned to the missing fields.

Missing day only

- If the month and year are the **same** as the year and month of first dosing date, then the first dosing date will be assigned to the missing day.
- If either the year of the partial date is **before** the year of the first dosing date or the years of the partial date and the first dosing date are the same but the month of partial date is **before** the month of the first dosing date, then the last day of the month will be assigned to the missing day.
- If either the year of the partial date is **after** the year of the first dosing date or the years of the partial date and the first dose date are the same but the month of partial date is **after** the month of the first dosing date, then the first day of the month will be assigned to the missing day.

Missing day, month, and year

- No imputation is needed. The corresponding AE will be included as a TEAE.

1.2 Incomplete Stop Date:

If the imputed stop date is before the start date, then the imputed stop date will be equal to the start date.

Missing day and month

- If the year of the incomplete stop date is the **same** as the year of the last dosing date, then the day and month of the last dosing date will be assigned to the missing fields.
- If the year of the incomplete stop date is **prior to** the year of the last dosing date or prior to the year of the first dosing date, then December 31 will be assigned to the missing fields.

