- If the year of the incomplete stop date is **prior to** the year of the last dosing date but is the same as the year of the first dosing date, then the first dosing date will be assigned to the missing date.
- If the year of the incomplete stop date is **after** the year of the last dosing date, then January 1 will be assigned to the missing fields.

Missing day only

- If the month and year of the incomplete stop date are the **same** as the month and year of the last dosing date, then the day of the last dosing date will be assigned to the missing day.

- If either the year of the partial date is **not equal to** the year of the last dosing date or the years of the partial date and the last dosing date are the same but the month of partial date is **not equal to** the month of the last dosing date, then the last day of the month will be assigned to the missing day.

2 Imputation of Dates for Prior/Concomitant Medications/Procedures

Partially missing start/stop dates for prior/concomitant medications and partially missing start dates for prior/concomitant procedures will be imputed in the ADaM dataset for prior/concomitant medications/procedures. However, listings of prior/concomitant medications/procedures data will present the date as is, with missing date components left blank.

For prior/concomitant medications, if the stop date is complete with no missing year, month, or day, and the partially missing start date imputed by the rule below is after the stop date, then the start date will be imputed by the stop date.

Partially missing prior/concomitant medication/procedure start dates will be imputed by the earliest possible date given the non-missing field(s) of the date.

Partially missing prior/concomitant medication stop dates will be imputed by the latest possible date given the non-missing field(s) of the date.

3. Imputation of Dates for Pre-specified Medical History

Partially missing start dates for pre-specified medical history will be imputed in the ADaM dataset for pre-specified medical history. However, listings of pre-specified medical history data will present the date as is, with missing date components left blank.

A partially missing pre-specified medical history start date will be imputed by the earliest possible date given the non-missing field(s) of the date and will be on or prior to the screening visit date.

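### Protocol and SAP put an adverse event that starts on the day of randomization and first blinded dose in different phases, and Appendix A counts an undated event as treatment-emergent even if it ended before blinded dosing

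*SAP*

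**What the plan says.** **Protocol 12.9** summarizes adverse events (AEs) in two groups. The first runs from the first Run-in dose through events starting "on or before the date of randomization; and (2) AEs with start date on the day after randomization". Read as from the day after randomization onward, the blinded phase therefore excludes the randomization date itself.

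**SAP 2.14.1** says: "An adverse event with onset date equivalent to the first dosing date will be considered to be treatment-emergent", and adds "unless there is evidence to conclude that it is not". The rule is introduced with "For subjects with the missing information for adverse events, the following imputation rules will be applied".

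**SAP 2.17.1** reports AEs separately for Run-in and the Blinded Treatment Phase. It gives no date that divides them and no definition of a treatment-emergent adverse event (TEAE).

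**SAP Appendix A, 1.1** covers incomplete AE start dates. If only the day is missing and the month and year match the first dose, "then the first dosing date will be assigned to the missing day". If the whole start date is missing: "No imputation is needed. The corresponding AE will be included as a TEAE".

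**SAP Section 3** lists the changes from the protocol: MRA concentration data, eGFR slope and the added Run-in analyses. AE phase assignment is not among them.

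**The concern.** This is a randomized withdrawal design. Up to the first blinded dose every subject is on Run-in patiromer, at least one packet a day (protocol 5.4). Day 1 is the hinge between that common exposure and the randomized comparison. Protocol 8.2 makes it both at once: "The qualifying Run-in Phase visit will become the Day 1/Baseline Visit". Serum K+ is drawn that day before the blinded dose (protocol 4.1 and 6.7.1.2), and AEs are assessed at the same visit (8.2.1).

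An AE dated Day 1 may therefore belong to Run-in patiromer or to the randomized treatment. If Run-in events are counted in the Treatment Phase, they enter both arms and blur the contrast. If the protocol boundary is used instead, true post-dose Day 1 events drop out of the randomized tables. The governing documents should give one answer, and at present they give two.

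Key secondary endpoint 3, investigator-reported hyperkalemia events, also needs a start rule. SAP 2.10.2 gives the model and the follow-up offset but does not say from which date an event counts.

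**Working it through.** The plan states no figure on this point, so the check sets the rules side by side.

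**Step 1: do the dates coincide?** Protocol 6.5 and SAP 1.3 place randomization on Day 1. SAP 2.13 takes the first dose of patiromer/placebo as its reference date, calls it Day 1, and in the same section describes it as the date of blinded study drug. Blinded drug is dispensed at the Day 1 visit (protocol 8.2.1). The dates normally coincide.

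**Step 2: apply both rules**, taking *first dosing date* as the first blinded dose.

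| Timing of first blinded dose | AE onset | Protocol 12.9 | SAP 2.14.1 with 2.13 | Agree? |
|---|---|---|---|---|
| Same day as randomization | Earlier day | Run-in | Not a Treatment Phase TEAE | Yes |
| Same day | That day, timing unknown | Run-in | TEAE | **No** |
| Same day | That day, documented after dose | Run-in | TEAE | **No** |
| Same day | That day, documented before dose | Run-in | Not a TEAE (exception) | Yes |
| Same day | Later day | Treatment Phase | TEAE | Yes |
| One or two days later | Randomization date | Run-in | Not a TEAE | Yes |
| Two days later | The day between | Treatment Phase | Not a TEAE | **No** |

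The conflict is confined to the shared date, plus an uncommon gap case when dosing is delayed.

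**Step 3: partial start dates.** An AE known only to have begun in the first-dose month is imputed to the first dosing date. If day and month are both missing and the year matches, it goes to the same date. Run-in lasts up to 12 weeks, so a Run-in event can be moved onto the contested day, where evidence of pre-dose timing is least likely to exist. Appendix A limits this: if a complete stop date precedes the imputed start, the start is set back to the stop date.

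**Step 4: fully missing start dates.** That stop-date check is worded for partially missing starts only. An AE with no start date and a complete stop date before the first blinded dose cannot have begun in the Treatment Phase, yet it is counted as a TEAE. The rule does not name a phase.

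**Step 5: which first dose?** SAP 2.17.1 also tabulates AEs for the Run-in Phase Set. Under SAP 2.1.4 those subjects were never randomized, so they have no blinded dose date. Appendix A needs a different anchor for them but uses one undefined term.

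**Step 6: direction of any effect.** Suppose a fraction *c* of subjects in each arm has a pre-dose event counted in error, independently of true events, and the true proportions are p1 and p0. Each observed proportion is p + c(1 − p), so the observed difference is

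[p1 + c(1 − p1)] − [p0 + c(1 − p0)] = (1 − c)(p1 − p0).

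The difference shrinks by the factor (1 − c) and the ratio moves toward 1. For mean event counts m1 and m0 with the same addition *a* in each arm, the difference is unchanged and (m1 + a)/(m0 + a) is closer to 1 than m1/m0. Neither *c* nor *a* can be obtained from the documents.

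**Step 7: stop dates.** In Appendix A, 1.2, take a stop date with day and month missing, in the first-dose year and before the last-dose year. One bullet gives 31 December. The next, for a stop year before the last-dose year "but is the same as the year of the first dosing date, then the first dosing date will be assigned to the missing date". Both apply to the same record. SAP 2.17.1 plans counts and percentages, not durations, and AE listings show dates as recorded.

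**The case against.** A reader might infer that the SAP routinely charges pre-dose Day 1 findings, such as a low magnesium on Run-in patiromer, to the randomized arms. The text does not support that. The exception lets a documented pre-dose finding be excluded, and a sample that the protocol requires before dosing is a clear case for it. What remains is that the SAP does not say what counts as evidence or who decides, and that the default governs events of unknown timing, including imputed dates.

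A reader might also infer a measurable dilution of key secondary endpoint 3. SAP 2.10.2 mentions neither TEAE status nor the Day 1 rule. In protocol 10.5.4 the K+ >5.0 reporting instruction sits within the criterion on changes to study treatment, and the same section says that not every abnormal result is an AE. Local K+ must be 4.0–5.0 at randomization. The documents give no local–central variability and no event rate, so no size can be attached. Only the missing start rule stands.

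The Day 1 sentence is an imputation rule for missing information, not a phase-assignment rule. If *first dosing date* meant the first Run-in dose, it would agree with protocol 12.9. That is fair, but SAP 2.13 points to the blinded dose, and on the other reading the SAP would have no rule for Day 1 at all.

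Finally, safety analyses are descriptive (SAP 2.17), undated events are probably few, and the stop-date overlap feeds no planned summary. All of this stands and limits the weight of the point.

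**Conclusion.** The point holds in a narrow form. When randomization and first blinded dose fall on the same day, an AE starting that day is Run-in under protocol 12.9 and, by default, treatment-emergent under SAP 2.14.1. The departure is undeclared. Appendix A moves some partially dated events onto that date and counts an undated event as a TEAE even when its stop date rules out onset in the Treatment Phase.

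The effect is likely to be small and similar in both arms: some dilution of AE contrasts, not a bias favoring one arm. The documents give no figure for it. This rests on reading *first dosing date* as the first blinded dose, on reading the undated-event rule as applying to Treatment Phase tables, and on misassignment being unrelated to arm. It is still worth correcting, because stated rules would misplace events in the randomized tables and a confirmatory count lacks a start rule.

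**What to change.** In the SAP, before unblinding:

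1. **Phase boundary.** Define a Treatment Phase TEAE as onset on or after the first blinded dose date, and assign a Day 1 finding from a pre-dose assessment to Run-in. Apply the same start rule to the count in key secondary endpoint 3. List the departure from protocol 12.9 in SAP Section 3.
2. **Appendix A, start dates.** Do not count an undated AE as a Treatment Phase TEAE when its stop date is before the first blinded dose. State that *first dosing date* means the first blinded dose for Treatment Phase tables and the first Run-in patiromer dose for Run-in tables.
3. **Tidying.** Reconcile the two overlapping stop-date bullets in Appendix A, 1.2.

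The cost is a few sentences and small derivation changes, with no new data. Protocol 12.1 leaves detailed methods to the SAP, so no protocol amendment is needed.

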2.14.2 Missing Dates or Partially Missing Dates

Missing or partially missing dates will be imputed conservatively for prior and concomitant medications/procedures, medical history, and adverse events. Specific rules for handling missing or partially missing dates are provided in "Appendix A: Imputation of Dates". Appendix A: Imputation of Dates

No imputations for any other missing safety data will be undertaken.

2.15 Subgroup Analyses

Descriptive analyses (including the presentation of 95% confidence intervals) will be produced for the subgroups specified below for the primary and key secondary endpoints. These descriptive analyses will be summarized graphically through the use of forest plots.

The key subgroups to be analysed are:

- At screening, hyperkalemic vs normokalemic with a history of hyperkalemia
- BMI
- Ejection fraction (< versus \geq median observed value)
- AF ongoing at screening (Yes versus No)
- Ischemic vs non-ischemic
- Screening use of ARNi (Yes versus No)
- Screening use of MRA (Yes versus No)
- Screening comorbidity:
 - Diabetes mellitus (Yes versus No)
- Baseline comorbidity:
 - CKD stage
 - eGFR \geq 60 versus < 60
 - eGFR \geq 45 versus < 45
 - NYHA class (II vs III-IV)
- Region (D vs A, B, C)
- Sex (Male or Female)
- Age (< versus \geq median observed value)
- NT-proBNP at screening (\leq versus $>$ median observed value)

The following subgroups will also be analysed:

- History of AF (Yes versus No)
- Region
 - US vs Non-US
 - Georgia + Ukraine vs all other countries

Note: depending on actual patient recruitment, additional comparisons between other regions, e.g., Latin America, Western Europe, Eastern Europe, Japan may be conducted

- Age < 65 versus \geq 65
- Age < 75 versus \geq 75
- Age < 80 vs \geq 80

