12.8.5 Subgroups of Interest

Descriptive analyses (including the presentation of 95% CIs) will be produced for the subgroups specified below. These descriptive analyses will be summarized graphically through the use of forest plots.

Subgroups to be analyzed include:

- At Screening, hyperkalemic versus normokalemic with a history of hyperkalemia
- Screening use of ARNi (Yes or No)
- Screening use of eplerenone or spironolactone (Yes or No)
- Screening comorbidity:
 - Diabetes mellitus (Yes or No)
 - CKD stage (Stage 3b versus Stages 1–3a, Stage \leq 3a versus Stage \geq 3b, Stage 4 versus Stage $<$ 4)
 - NYHA Class (II versus III–IV)
- Region (US versus Non-US)

Note: Depending on actual subject recruitment, additional comparisons between other regions, e.g., Latin America, Western Europe, Eastern Europe, will be defined in the SAP

- Gender (male or female)

- Age (age group categories will be defined prior to unblinding)
- Race/ethnicity (limited to racial/ethnic subgroups that comprise 20% or more of the study population)
- Median NT-proBNP at Screening

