1.3 Method of Assigning Subjects to Treatment Groups

Subjects will be randomized to the treatment arms (1:1 assignment) using permuted block randomization stratified by region. Randomization will take place using a centralized list accessed electronically on the day of randomization after Double-Blinded Treatment Phase eligibility is determined (Day 1).

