1.5 Sample Size

The sample size of 410 subjects per treatment arm (total of 820 subjects) has been calculated to provide 90% power to detect a difference between the control group (placebo) and the active group (patiromer) in change in K^+ levels from Baseline. This sample size calculation is based upon the following assumptions: alpha level of 5% (2-sided); difference between group means of 0.116; a SD of 0.5; and 5% loss to follow-up.

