3 CHANGES FROM THE PROTOCOL

The protocol specifies that blood samples be taken during the study in order to analyse subject MRA levels.

The complete, validated MRA concentration data will not be available at the time of database lock, and analyses of that data will not be included for the CSR. The complete and validated data will be delivered later and analysed separately.

Slope of eGFR change during the study was proposed as a safety endpoint in the protocol. In the SAP it has been changed to an efficacy endpoint, and will be analysed using an mrrm model similar to those used for other efficacy endpoints.

Analyses during Run-in have been added to the SAP.

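### The SAP's 21 subgroup splits are reported by level-specific estimates and 95% CIs only; no treatment-by-subgroup estimate is specified, so the difference between levels is not directly reported.

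*SAP*

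**What the plan says.** SAP 2.15 sets the method in two sentences. The first is "Descriptive analyses (including the presentation of 95% confidence intervals) will be produced for the subgroups specified below for the primary and key secondary endpoints", and the second is "These descriptive analyses will be summarized graphically through the use of forest plots". Fifteen key splits and six further splits follow, 21 in all if CKD stage is read as the heading of the two eGFR cuts (22 if it is counted separately). BMI has no cut-point. No redaction is marked in the section. The only interaction named in the readable SAP is treatment by visit, in 2.10.1.

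Protocol 12.8.5 takes the same approach: "Descriptive analyses (including the presentation of 95% CIs) will be produced for the subgroups specified below". Its list includes "Race/ethnicity (limited to racial/ethnic subgroups that comprise 20% or more of the study population"). SAP 2.15 has no race or ethnicity subgroup, although SAP 2.5 still summarises both as demographics. SAP Section 3 declares changes on MRA concentration data and the eGFR slope, and ends with "Analyses during Run-in have been added to the SAP". It mentions no subgroup change.

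**The concern.** A subgroup forest plot is read to see whether the treatment effect differs between levels. The plan supplies an estimate and interval for each level but not the contrast between them. Without that contrast, readers tend to note which intervals cross the null, and that depends heavily on how many subjects each level contains.

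With 21 splits on six endpoints (one primary, five key secondary), an effect that is the same everywhere could be misread as absent in one sex, region or eGFR group. A real difference between levels would have no estimate or interval of its own on the page.

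**Working it through.** **Inputs.** SAP 1.5: "alpha level of 5% (2-sided); difference between group means of 0.116; a SD of 0.5; and 5% loss to follow-up". Sample size, same section: "The sample size of 410 subjects per treatment arm (total of 820 subjects) has been calculated to provide 90% power". Allocation, SAP 1.3: "Subjects will be randomized to the treatment arms (1:1 assignment) using permuted block randomization stratified by region". Subgroup shares are not in the documents, so even and 20/80 splits are used as assumptions. Numbers analysed at the June 24, 2021 cut-off are not given either, so the planned size is used.

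**1. Reproduce the plan's figure.** n per arm = 2(1.960 + 1.282)² × 0.5² / 0.116² = 390.4, so 391. Dividing by 0.95 gives 412, against 410 stated. With 410 × 0.95 = 389.5 per arm, SE = 0.5√(2/389.5) = 0.0358, z = 0.116/0.0358 = 3.24, and power is 89.9%. The stated 90% reproduces.

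**2. Uniform effect of 0.116, even split.** Per arm and level, n = 194.75. SE = 0.5√(2/194.75) = 0.0507, z = 2.29, power p = 0.629.
- Exactly one level's CI excludes zero: 2 × 0.629 × 0.371 = 0.467.
- Both include zero: 0.371² = 0.138. The two levels then agree, so this case is not counted as apparent inconsistency.

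**3. Uniform effect, 20/80 split.** Per arm, n = 77.9 and 311.6. SEs are 0.0801 and 0.0401, and powers are 0.304 and 0.825.
- Exactly one excludes zero: 0.304 × 0.175 + 0.825 × 0.696 = 0.627.
- Both include zero: 0.696 × 0.175 = 0.122.

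**4. Effect of repeated visits.** Steps 2 and 3 treat the outcome as one measurement. The primary MMRM (SAP 2.10.1) estimates one treatment effect across visits, and the protocol's Schedule of Events has local K⁺ at Day 3 and Weeks 1, 2, 6 and 18. Assume that SD 0.5 applies per visit and that five visits are complete, equally weighted and equally correlated (ρ). The variance is then multiplied by (1 + 4ρ)/5:

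| ρ (assumed) | Factor | Exactly one excludes zero, even | Exactly one excludes zero, 20/80 |
|---|---|---|---|
| single measurement | 1 | 47% | 63% |
| 0.7 | 0.76 | 38% | 60% |
| 0.5 | 0.60 | 27% | 53% |
| 0.3 | 0.44 | 13% | 41% |

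The documents give no ρ and do not say whether 0.5 is a per-visit SD.

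**5. What an interaction estimate would offer.** Single-measurement basis, even split: SE = √(0.0507² + 0.0507²) = 0.0717, so the 95% CI half-width is 1.96 × 0.0717 = 0.14 mEq/L, wider than the 0.116 design effect. Under a uniform effect each split has a 5% chance of a nominal signal. Over 21 splits on one endpoint, 21 × 0.05 = 1.05 are expected, and the chance of at least one is 1 − 0.95²¹ = 66% if the splits are independent.

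**The case against.** The strongest reply is that the SAP does not tell anyone to judge consistency by whether intervals cross zero. It calls the analyses descriptive, presents the CIs as one part of them, and states no reading rule. The protocol uses the same approach, so nothing has been departed from. All of this stands. A reader might infer that the plan judges its subgroups only by separate CIs, but the text does not say so. The gap is the absence of both a contrast and a reading rule.

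Second, one might headline the chance that at least one level's CI includes zero: 60% for an even split and 75% for 20/80. Those figures count splits where both levels cross zero and so agree. They overstate apparent inconsistency, and exactly one level excluding zero is the relevant event.

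Third, the repeated visits could cut the even-split figure from 47% to 27% or 13% at assumed correlations of 0.5 or 0.3. This also stands. How often the problem arises depends on inputs that the documents omit.

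Fourth, for disjoint levels a reader can approximate the difference from the two published estimates and CIs. That is true, so the information is not lost. It is merely not displayed.

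Finally, a reader might take the missing race/ethnicity subgroup as an undeclared removal of a promised analysis. The protocol makes it conditional on a 20% share, and the documents give no racial composition, so it may simply not qualify. Its absence has no bearing on whether other subgroups look inconsistent. Nor do the added regional comparisons show a departure, since protocol 12.8.5 leaves further regional comparisons to the SAP.

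**Conclusion.** The point holds as a cheap improvement to the plan. It is neither an error in the plan nor a breach of the protocol. SAP 2.15 does not directly report the difference between levels for any of its 21 splits.

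The size is bounded above by the single-measurement figures: about 47% of even splits and 63% of 20/80 splits would show exactly one level excluding zero under a uniform effect. Under the assumptions in step 4, correlations of 0.3 to 0.7 give 13% to 38% and 41% to 60%. These figures rest on the planned sample size, assumed subgroup shares and the primary endpoint only. No calculation was made for the five key secondary endpoints.

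An interaction estimate lowers the nominal false-signal rate to 5% per split. It does not remove false signals across 21 splits, and it will be imprecise. On race/ethnicity, the only defect is a missing explanation, and it is minor.

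**What to change.** In SAP 2.15:
- For the MMRM, Cox and negative binomial endpoints, fit the planned model in the full analysis set with the subgroup and a treatment-by-subgroup term. Take the level-specific estimates from that fit, and show the interaction estimate with its 95% CI on each forest-plot row.
- For the two win-ratio endpoints, show the ratio of the level-specific win ratios with its CI.
- State that consistency is read from that estimate, not from whether a level's own CI crosses the null.
- State that it is exploratory and not adjusted for multiplicity, with about one nominal false signal expected per 21 splits on one endpoint, and that intervals will be wide.

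Separately, in SAP Section 3, say why the race/ethnicity subgroup is absent, or restore it in 2.15 with the protocol's 20% condition.

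The cost is SAP wording, one interaction term per subgroup model and a ratio calculation for the win ratios. No new data are needed. The downside is 21 × 6 = 126 further estimates, many of them imprecise, which is why the caution belongs beside the plots.
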